2.2 Secondary Objectives

To evaluate the efficacy of etanercept plus methotrexate therapy compared to methotrexate monotherapy on maintenance of remission.

To evaluate the efficacy of 1) etanercept monotherapy compared to methotrexate monotherapy and 2) etanercept plus methotrexate therapy compared to methotrexate monotherapy on:

- disease activity
- disease-worsening and time to disease-worsening
- remission and time to recapture remission after rescue treatment

2.3 Safety Objective

To evaluate the safety of etanercept and methotrexate

2.4 Exploratory Objectives

- To evaluate Patient Reported Outcomes (PRO)
- To investigate potential biomarkers of disease activity and response to etanercept.
- To investigate the effects of genetic variation in disease genes and drug target genes on RA and/or subject response to etanercept.

3. Study Overview

3.1 Study Design

This is a Phase 3, multicenter, randomized withdrawal, double-blind controlled study in subjects with RA on etanercept plus methotrexate who are in very good disease control for 6 months prior to study entry. The study will consist of a 30-day screening period, a

24-week open-label run-in period, a 48-week double-blind treatment period and a 30-day safety follow-up period.

The study will enroll approximately 358 subjects. During the run-in period subjects will receive open-label etanercept and methotrexate at the same dose they were receiving during screening. It is expected that approximately 30% of subjects will early terminate the run-in period. Amgen may choose to alter the sample size of subjects enrolled in order to ensure that approximately 250 subjects are randomized to treatment.

Approximately 250 subjects will be randomly assigned in a 2:2:1 ratio to one of three treatment groups:

- Etanercept 50 mg weekly by subcutaneous injection plus oral placebo for methotrexate (n = 100)
- Oral methotrexate 10 to 25 mg weekly plus placebo for etanercept (n = 100)
- Etanercept 50 mg weekly by subcutaneous injection plus oral methotrexate 10 to 25 mg weekly (n = 50)

Subjects randomized to the etanercept plus methotrexate group and the methotrexate monotherapy group will receive methotrexate at the same dose they were receiving at screening and during the run-in period.

3.2 Sample Size

The sample size was determined from a hypothesis of superiority of etanercept monotherapy over methotrexate monotherapy. The proportion of subjects achieving SDAI remission after 52 weeks of double-blind treatment in the PRESERVE and COMET studies was used to estimate the treatment effects. PRESERVE was a two-period study conducted in subjects with RA who had moderate disease activity despite a stable dose of oral methotrexate for a minimum of 8 weeks at the time of screening. Among all subjects who were in SDAI remission at both week 28 and week 36 (the last two visits of the open-label run-in period), the proportion of subjects who were still in remission after the 52-week double-blind period was 86.1% and 38.1% for the etanercept plus methotrexate therapy and methotrexate monotherapy treatment groups, respectively. COMET was a two-period study conducted in subjects with active early RA. Among all subjects who received etanercept plus methotrexate therapy in Period 1 and were in SDAI remission at week 52, the last visit of Period 1, the proportion of subjects who were in still in remission after the 52-week double-blind Period 2 was 78.3% and 72.4%, respectively, for the etanercept plus methotrexate therapy and etanercept monotherapy treatment groups. Given key differences noted in this study, including the sustained period of remission prior to withdrawal, the response rate in the methotrexate monotherapy arm is approximated to be higher at 50%, with the response

rate in the etanercept monotherapy arm at approximately 72%. It is expected that compared to PRESERVE, subjects in the current study will have more stable disease at the time of randomization. Namely, subjects must be in very good disease control for 6 months prior to study entry and must be in SDAI remission at the end of a 24-week open-label run-in period.

The sample size is based on the adequacy to evaluate the efficacy of etanercept monotherapy compared to methotrexate monotherapy as measured by the primary endpoint of SDAI remission at week 48 at a significance level of 0.05. The sample size was also ensured to be sufficient to evaluate the efficacy of the etanercept plus methotrexate treatment arm compared to methotrexate monotherapy. Based on a two-sided chi-square test with 90% power, 100 subjects per arm are required at randomization.

Using an assumed attrition rate of 30% in the open-label run-in period, due to exclusion of subjects with Disease-Worsening during the run-in period, or other reasons, approximately 358 subjects will be enrolled in order to have approximately 250 subjects randomized in a 2:2:1 ratio to one of three treatment groups: etanercept monotherapy (n = 100), methotrexate monotherapy (n = 100) and etanercept plus methotrexate combination therapy (n = 50). Amgen may choose to alter the sample size of subjects enrolled in order to ensure that approximately 250 subjects are randomized to treatment.

4. Study Endpoints and Covariates

4.1 Study Endpoints

4.1.1 Primary Endpoint

- SDAI remission (≤ 3.3) at week 48

The primary estimand consists of:

- Target population – patients with a history of moderate to severe rheumatoid arthritis (RA) who are on etanercept and methotrexate combination therapy and who are in very good disease control.
- Endpoint – SDAI remission (SDAI \leq 3.3) at week 48
- Intercurrent events – there are 2 intercurrent events: first, discontinuation of IP before week 48; second, disease-worsening after randomization which triggers initiation of rescue therapy. Treatment effects will be estimated for subjects regardless of whether subjects complete 48 weeks of IP.
- Summary measure – difference in the proportion of subjects achieving SDAI \leq 3.3 (yes/no) at Week 48 on etanercept monotherapy and that of subjects achieving SDAI \leq 3.3 (yes/no) at Week 48 on methotrexate monotherapy.

In summary, the primary estimand is the difference in proportions of subjects in etanercept monotherapy and methotrexate monotherapy maintaining SDAI remission at Week 48 without experiencing disease-worsening on study in adults with a history of moderate to severe RA who have been on etanercept and methotrexate combination therapy and in very good RA disease control, regardless of adherence to treatment and completion of 48 weeks of IP.

4.1.2 Secondary Endpoints

- SDAI score and change from baseline at all measured timepoints
- DAS-28-ESR and change from baseline at all measured timepoints
- DAS-28-CRP and change from baseline at all measured timepoints
- CDAI and change from baseline at all measured timepoints
- SDAI remission (≤ 3.3) at all measured timepoints
- Boolean remission at all measured timepoints
- Disease-Worsening defined as an SDAI > 3.3 and ≤ 11 during two consecutive visits at least 2 weeks apart or SDAI > 3.3 and ≤ 11 on three or more separate visits or SDAI > 11 after randomization
- Time to Disease-Worsening as an SDAI > 3.3 and ≤ 11 during two consecutive visits at least 2 weeks apart or SDAI > 3.3 and ≤ 11 on three or more separate visits or SDAI > 11 after randomization

In subjects that receive rescue treatment during the double-blind treatment period

- Time to recapture SDAI remission after starting rescue treatment
- SDAI remission at week 48

4.1.3 Safety Endpoints

- Adverse events
- Serious adverse events
- Laboratory parameters

4.1.4 Exploratory Endpoints

- Components of SDAI at all measured timepoints
- HAQ-DI at all measured timepoints
- SF-36 domains, physical component summary, and mental component summary at all measured timepoints

Additional exploratory endpoints pertaining to the Run-In Period are:

- SDAI score at run-in visits
- Time to run-in failure
- Time to randomization failure

Additional exploratory endpoints pertaining to the Double-Blind Period are:

- Observed SDAI Remission (≤ 3.3) at all timepoints
- Patient Global Assessment of Joint Pain at all timepoints
- SDAI LDA at all timepoints
- DAS28-ESR remission at all timepoints
- DAS28-ESR LDA at all timepoints
- DAS28-CRP remission at all timepoints
- Reason for Disease-Worsening
- SDAI score at Disease-Worsening
- Disease Activity at Disease-Worsening

In subjects that receive rescue treatment and in subjects that fulfill disease-worsening criteria during the double-blind treatment period:

- Observed SDAI remission (yes/no) at visits following rescue
- SDAI LDA (yes/no) at visits following rescue
- Time to SDAI LDA
- SDAI score on Disease-Worsening Date and at subsequent visits
- Change in SDAI from Disease-Worsening Date and at subsequent visits
- DAS28-ESR remission (yes/no) at visits following rescue
- Time to DAS28-ESR remission
- DAS28-ESR LDA (yes/no) at visits following rescue
- DAS28-CRP remission (yes/no) at visits following rescue
- Time to DAS28-CRP remission.

4.2 Planned Covariates

The following baseline covariates will be considered to assess their influence on the primary and secondary endpoints:

- age (years) (continuous)
- sex (male, female)
- race (Caucasian, non-Caucasian)
- ethnicity (Hispanic or Latino vs Non-Hispanic or Latino)
- disease duration (in years)
- baseline methotrexate dose (continuous)
- additional covariates will be evaluated (baseline methotrexate dose [<15 mg / ≥ 15 mg], smoking [never, former, current])

The rationale for inclusion of baseline methotrexate dose [<15 mg / ≥ 15 mg] and smoking status is provided in [Section 12](#).

Subgroup analyses, which would be considered exploratory, may be performed if an examination of the above covariates suggests that any treatment difference for the primary and secondary endpoints depends on any baseline covariates.

5. Hypotheses and/or Estimations

There are two clinical hypotheses. First,

Etanercept monotherapy is superior to methotrexate monotherapy for maintaining remission in subjects with RA who were on etanercept plus methotrexate therapy as measured by the proportion of subjects who maintain SDAI remission ($SDAI \leq 3.3$) at week 48.

Specifically, the null (H_0) and alternative (H_1) hypotheses are defined as follows:

H_0 : The difference in proportion of subjects who maintain SDAI remission at week 48 in the etanercept monotherapy arm and in that of the methotrexate monotherapy arm = 0

H_1 : The difference in proportion of subjects who maintain SDAI remission at week 48 in the etanercept monotherapy arm and in that of the methotrexate monotherapy arm $\neq 0$.

Second,

Etanercept and Methotrexate combination therapy is superior to methotrexate monotherapy for maintaining remission in subjects with RA who were on etanercept plus methotrexate therapy as measured by the proportion of subjects who maintain SDAI remission ($SDAI \leq 3.3$) at week 48.

Specifically, the null (H_0) and alternative (H_1) hypotheses are defined as follows:

H_0 : The difference in proportion of subjects who maintain SDAI remission at week 48 in the etanercept and methotrexate combination arm and in that of the methotrexate monotherapy arm = 0

H_1 : The difference in proportion of subjects who maintain SDAI remission at week 48 in the etanercept and methotrexate combination arm and in that of the methotrexate monotherapy arm $\neq 0$.

6. Definitions

6.1 Study Time Points

Enrollment Date

A subject's Enrollment Date is defined as the date he or she has met all Part 1 eligibility criteria and the enrollment call in the IXRS system has been completed.

Part 1/Run-in Period

The 24-week period after enrollment and prior to randomization. Specifically, the period begins when a subject initiates treatment with open-label run-in etanercept and/or open-label run-in methotrexate per the eCRF at the same dose he or she was receiving at screening. There are three visits associated with the Run-in Period: Run-in Visit 1, Run-in Visit 2, and Run-in Visit 3.

Run-In Day 1

A subject's Run-In Day 1 is defined as the date of the first dose of IP administration during Part 1.

Run-In Day

A subject's Run-In Day = (Visit Date – Run-In Day 1 date) + 1.

Run-In Failure Date

A subject's Run-In Failure Date is the date the subject ended run-in due to protocol specified criteria per the eCRF.

Randomization Failure Date

A subject's Randomization Failure Date is the date the subject ended run-in due to any reason and was not randomized.

End-of Run-In Date

A subject's End-of Run-In Date is the date subject ends the run-in period per the CRF.

Randomization Date

A subject's Randomization Date is the date when a randomization number is assigned to him or her through the Interactive Voice/Web Response System (IXRS).

Study Day 1

A subject's Study Day 1 is defined as the date of the first dose of IP administration after randomization, or the randomization date if the subject is not dosed.

Baseline

The last measurement for the endpoint of interest taken on or prior to Study Day 1 and after Run-In Visit 3. Hematology and chemistry profiles were not assessed on Day 1; their Run-in Visit 3 values will be used when reporting baseline.

Baseline for Concomitant Medications

Run-In Period Baseline for Concomitant Medications is enrollment date, and Post-Run-In Period Baseline for Concomitant Medications is randomization date.

Study Day

For a given study visit, the study day for a subject is defined as:

Study Day = (Visit Date – Study Day 1 date) + 1.

Part 2/Treatment Period

The up-to 48-week double-blind period beginning with Study Day 1 and ending with the End of Study date.

SDAI Assessment Datea

The SDAI Assessment Date is the latest date of the assessments for Tender Joint Count, Swollen Joint Count, Physician Global Assessment, Patient Global Assessment, and CRP for a given SDAI score.

Disease-Worsening Date (DW Date)

A subject's Disease-Worsening Date is the first Visit Date in which the subject meets the definition for Disease-Worsening. With the exception of analysis using multiple imputation method, Disease-Worsening classification is based on observed SDAI values only. Each subject will have at most one DW Date. A subject's disease-worsening date is used to define his/her Disease-Worsening Baseline.

Rescue Date

A subject's rescue date is the Visit Date in which he or she first receives rescue therapy as identified by the Investigational Product Administration (Rescue Therapy Etanercept) or Investigational Product Administration (Rescue Therapy Methotrexate) form.

Rescue Therapy Period

For the Rescue Analysis Set as defined in [Section 7.4](#), the Rescue Therapy Period begins with the Rescue Date through the EOS Date.

Disease-Worsening Analysis Visit (DW_visit)

The DW_visit defines the analysis visit after a subject fulfills disease-worsening criteria. Details of DW_visit derivation are in [Appendix A](#).

Rescue Analysis Visit (Rescue_visit)

Rescue_visits define the analysis visits after a subject initiates rescue therapy. Details of Rescue_Visit derivation are in [Appendix A](#).

End of Treatment (EOT)

The End of Treatment for a subject is the subject's last assessment for the protocol-specified treatment phase of the study.

End of Study Date

The End of Study Date for a subject is the date the subject completes the safety follow-up phone call, or the date of the Early Termination (ET) visit if no safety follow-up phone call is completed. The date the subject has ended the study is recorded on the End of Study Electronic Case Report Form (eCRF).

End of Study

The End of Study is the date when the last subject across all sites is assessed or receives an intervention for evaluation in the study (ie, last subject last visit).

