#### **4.2 Inclusion and Exclusion Criteria – Part 2**

##### **4.2.1 Inclusion Criteria – Part 2**

- 116 SDAI  $\leq$  3.3 at run-in visit 3
- 117 Subject if female and not at least 2 years postmenopausal or history of hysterectomy, bilateral salpingectomy, or bilateral oophorectomy, has a negative urine pregnancy test at baseline (day 1).

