**Table 1. Schedule of Assessments**

	30-day Screening	Open-Label Run-in Period h				Double Blind Treatment Period g						Follow-Up
Weeks		Run-in Visit 1	Run-in visit 2	Run-in visit 3	Run-in ET	0 g	12	24	36	48/ET	Disease Assessment e	Safety (EOS) i
Days	-198 (from Day 1)	-168 (from Day 1)	-84 (from Day 1)	-7 (from Day 1)		Day 1						30
DOSING												
Etanercept/placebo for etanercept dispensation		X	X			X	X	X	X		X f	
Methotrexate/placebo for methotrexate dispensation		X	X			X	X	X	X		X f	
Dispense dosing diary		X	X			X	X	X	X			
Review dosing diary			X	X	X	X	X	X	X	X	X	
DISEASE ASSESSMENTS												
66 Swollen joint count	X	X	X	X		X	X	X	X	X	X	
68 Tender joint count	X	X	X	X		X	X	X	X	X	X	
Physician global assessment of disease activity	X	X	X	X		X	X	X	X	X	X	
SUBJECT ASSESSMENTS (PRO)												
Patient global assessment of joint pain	X	X	X	X		X	X	X	X	X	X	
Patient global assessment of disease activity	X	X	X	X		X	X	X	X	X	X	
Disability Index of the Health Assessment Questionnaire (HAQ-DI)						X		X		X		
Medical Outcomes Short Form-36 Questionnaire (SF-36)						X		X		X		

ET = early termination; ESR = erythrocyte sedimentation rate; EOS = end of study; HBV = hepatitis B virus; PCR = polymerase chain reaction.

a Screening physical exam will be a full exam; subsequent exams per standard of care to monitor for any changes

b For all women, unless at least 2 years postmenopausal or history of hysterectomy, bilateral salpingectomy, or bilateral oophorectomy

c Additional pregnancy testing may be completed at the discretion of the investigator

d Subjects will receive either a PPD test or Quantiferon test at screening. National guidelines should be followed for appropriate tuberculosis screening in the setting of anti-TNF therapy.

e Disease Assessment Visit - disease activity may be assessed at a regularly scheduled visit or at a Disease Assessment visit as described in [Section 7.2.7](#)

f If subjects meet the criteria for disease worsening then etanercept plus methotrexate will be dispensed at the same dose they were receiving at screening

g Baseline (Day 1) visit must be scheduled ≤7 days from the run-in visit 3

h Visit window is +/- 7 days for all visits after screening

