10.3.1 Missing Baseline Evaluation

Missing baseline evaluations will not be imputed.

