10.3.3 Missing Components of Composite Endpoints

Missing components of composite endpoints will not be imputed.

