11.5.2 Secondary Efficacy Endpoint(s)

For secondary endpoints, unless otherwise noted, the Chi-squared test will be used for categorical endpoints, the t-test for continuous endpoints, and Log-rank test for time-to-event endpoints. In comparison of means, the Satterthwaite t-test may be used when variances between the two groups are different. These tests will evaluate etanercept monotherapy vs methotrexate monotherapy and etanercept and methotrexate combination therapy vs methotrexate monotherapy.

Proportion of subjects achieving SDAI remission at week 48 for the etanercept plus methotrexate treatment arm will be compared to that of the methotrexate monotherapy arm using the chi-squared test and will be presented with nominal p-values only (eg, no adjustment for multiplicity will be done). To parallel the the primary analysis of the primary estimand, the proportion of subjects in the etanercept plus methotrexate treatment arm and the methotrexate monotherapy arm achieving SDAI remission at week 48 will be evaluated using non-responder imputation, as observed data, and multiple imputation.

The proportion of subjects achieving SDAI remission (≤ 3.3), SDAI continuous score, and SDAI change from baseline at all visits will be summarized by treatment group using the PAS. Subjects with missing SDAI value at week 48 and subjects who disease-worsened are considered non-responders.

DAS28-ESR, DAS28-CRP, and CDAI, and their changes from baseline will also be summarized by visit for each treatment group using the PAS. Missing data will not be imputed for these continuous endpoints. T-tests will compare means between etanercept vs methotrexate and etanercept + methotrexate vs methotrexate.

Proportion of subjects achieving Boolean remission will be tabulated by visit for each treatment group using the PAS. Boolean remission using 28-joint-count, 28-joint-count + feet and ankles, and 66/68 joint count will be assessed.

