Per protocol, visits are to be performed within 7 days of the protocol-specified study day. To allow for variations in scheduling, the following visit windows will be applied to selected efficacy and safety evaluations (ie, vital signs, laboratory evaluations) to assign a most appropriate nominal visit for the analysis (ie, analysis visit). If more than one visit falls within the same defined window, the closest visit to the target day (ie, scheduled visit week $\times 7 + 1$) will be considered for analysis. If two assessment dates are the same distance from the target day, then the latest visit will be considered for analysis. If more than one evaluation exists on the same date and time, the record with the lower accession number will be used.

Run-In Period Visits

Visit Week	Target Day	Window Definition	Interval (days)
Run-in 1	Run-in Day 1	Last evaluation prior to or on Run-In Study Day 1 and after Enrollment Date	43+
Run-in 2	Run-in Day 86	Run-in Day 44 to 125	82
Run-in 3	Run-in Day 162	Run-in Day ≥ 126	43

Double-Blind Treatment Period Analysis Visits

Visit Week	Target Day	Window Definition	Interval (days)
Baseline	Study Day 1	Last evaluation prior to or on Study Day 1 and after Run-in Visit 3*	N/A
Week 12	Study Day 85	Study Day 2 to 126	125
Week 24	Study Day 169	Study Day 127 to 210	84
Week 36	Study Day 253	Study Day 211 to 294	84
Week 48	Study Day 337	\geq Study Day 295	N/A

* Hematology and chemistry profiles were not assessed on Day 1; their Run-in Visit 3 values will be used when reporting baseline.

Visit window for SF-36 and HAQ-DI

Visit Week	Target Day	Window Definition	Interval (days)
Baseline (Day1)	1	Last evaluation prior to or on study day 1 in DB	N/A
Week 24	169	Study Day 2 to 253	252
Week 48	337	\geq Study Day 254	n/a

Time After Disease-Worsening

Let $Visit_0$ = the Analysis Visit at which a subject fulfills disease-worsening criteria, where Analysis Visit is for SDAI score and is defined in the Double-Blind Treatment Period Analysis Visits Table above. $Visit_0$ will be summarized in tables as “Disease-Worsening Baseline”.

Let $Visit_1$ represent the Analysis Visit on or after $Visit_0$.

Then DW_visit will be defined as follows:

- $DW_visit = 12$,
If $Visit_1 - Visit_0 = 0$ or 12
- $DW_visit = Visit_1 - Visit_0$,
Otherwise.

If a subject has multiple observations for the same DW_Visit , the latest observation will be used in the analysis.

Time After Rescue

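### The efficacy baseline excludes Run-in Visit 3 and has no fallback, so a missing Day 1 component removes all change scores of each composite that uses it

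*SAP*

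**What the plan says.** SAP 6.1 sets baseline separately for each endpoint as "The last measurement for the endpoint of interest taken on or prior to Study Day 1 and after Run-In Visit 3". The double-blind visit-window table in SAP Appendix A has the same rule: "Last evaluation prior to or on Study Day 1 and after Run-in Visit 3". A Run-in Visit 3 value therefore cannot serve as an efficacy baseline. Both places make one exception, for laboratory panels: "Hematology and chemistry profiles were not assessed on Day 1; their Run-in Visit 3 values will be used when reporting baseline".

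Nothing fills a gap. SAP 10.3.1 says "Missing baseline evaluations will not be imputed" and SAP 10.3.3 says "Missing components of composite endpoints will not be imputed". For DAS28-ESR, DAS28-CRP and CDAI and their changes, SAP 11.5.2 adds "Missing data will not be imputed for these continuous endpoints".

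Change from baseline in SDAI, DAS28-ESR, DAS28-CRP and CDAI is a secondary endpoint at every visit (SAP 4.1.2). It is compared by t-test in the Primary Analysis Set (SAP 11.5.2 and Table 1), with no multiplicity adjustment (SAP 11.1).

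Protocol Table 1 schedules joint counts, both global assessments, CRP and ESR at Run-in Visit 3 and again on Day 1. Footnote g says the Day 1 "visit must be scheduled ≤7 days from the run-in visit 3", and Protocol 7.2.3 agrees. Inclusion criterion 116 (Protocol 4.2.1) requires SDAI of no more than "3.3 at run-in visit 3".

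**The concern.** The window for an efficacy baseline is short, and in practice it holds one planned visit, Day 1. If a component is lost there (a CRP sample that fails, a global assessment not entered), the composite has no baseline and no change score at any later visit, however complete the follow-up. A Disease Assessment visit between Run-in Visit 3 and Day 1 (Protocol 7.2.7) could supply a value, but none is routinely planned.

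The loss is avoidable. The same assessments were due up to a week earlier, on the same open-label treatment and before randomisation. The SAP gives no reason for setting that value aside, and its Section 12 on changes from the protocol does not mention it. At stake is a small number of randomised subjects dropping out of secondary change analyses. A second risk is that the choice of fallback is made after the data have been seen.

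**Working it through.** **1. The 7-day gap.** Protocol Table 1 puts Run-in Visit 1 at 168 days and Run-in Visit 3 at 7 days before Day 1. On the run-in scale:

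- Day 1 is 168 + 1 = Run-in Day 169.
- Run-in Visit 3 is 168 − 7 + 1 = Run-in Day 162, the target day in SAP Appendix A.
- The gap is 169 − 162 = 7 days, as in footnote g and Protocol 7.2.3.

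The SAP analysis window for Run-in Visit 3 is wider and opens at Run-in Day 126. A value assigned to that visit could be 169 − 126 = 43 days old if the protocol's scheduling were not followed. A fallback therefore needs its own age limit.

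**2. Which change scores are lost.** Inputs are the scoring formulas in SAP Appendix A and the no-imputation rule for components.

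| Missing on Day 1 | SDAI | CDAI | DAS28-CRP | DAS28-ESR |
|---|---|---|---|---|
| Tender count | lost | lost | lost | lost |
| Swollen count | lost | lost | lost | lost |
| Patient global | lost | lost | lost | lost |
| Physician global | lost | lost | kept | kept |
| CRP | lost | kept | lost | kept |
| ESR | kept | kept | kept | lost |

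Each loss covers weeks 12, 24, 36 and 48.

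**3. Whether a Run-in Visit 3 value exists.** Criterion 116 cannot be met without an SDAI, so an eligible randomised subject should have all five SDAI components from that visit. These also give CDAI and DAS28-CRP. ESR is scheduled there but not needed for eligibility, so a DAS28-ESR fallback is likely but not assured.

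**4. Size.** The documents give no rate of incomplete Day 1 data, so the rate m is an assumption, shown over a range. With 250 randomised:

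- subjects lost to an affected change analysis = 250 × m
- standard error ratio = 1/√(1 − m), for equal proportional loss in each arm and an unchanged standard deviation
- power of a comparison that would have had 90% = Φ[(1.960 + 1.282) × √(1 − m) − 1.960]; the 90% is illustrative, as the plan states no power for change scores

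| m | Subjects lost | Rise in standard error | Power, from 90% |
|---|---|---|---|
| 1% | 2.5 | 0.5% | 89.7% |
| 2% | 5 | 1.0% | 89.4% |
| 5% | 12.5 | 2.6% | 88.5% |
| 10% | 25 | 5.4% | 86.8% |

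For example, at 10%: 250 × 0.10 = 25 and 1/√0.90 = 1.054.

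**5. What is not affected.** SDAI remission at week 48 and other visits (SAP 6.2, 6.5), disease worsening (SAP 6.5) and time to worsening (SAP 6.4) are derived without a baseline value. Observed scores at each visit are also analysed without one.

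**The case against.** The strongest defence is that Day 1 only is a deliberate and defensible choice. Protocol 7.2.5 names Day 1 as the baseline visit, and Table 1 repeats every disease assessment then. Run-in Visit 3 is the selection visit: SDAI had to be 3.3 or less there, while the Part 2 criteria set no separate SDAI threshold for Day 1. A fallback would mix threshold-selected baselines with unselected ones and invite some regression to the mean. This stands as a small downside. It is not a reason to discard the value, because the selection precedes randomisation and applies to all arms alike. The SAP does not give it as its reason.

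Observed-case analysis of secondary endpoints is also pre-specified (Protocol 10.5.1). A reader might infer that losing these subjects breaches the all-randomised analysis set. The documents do not support that: subjects without a baseline stay in the set and contribute their observed scores.

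A reader might also take the laboratory rule as proof of inconsistency. That is weak. Haematology and chemistry use Run-in Visit 3 because they are not scheduled on Day 1, not as a rescue for missing data.

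Finally, the obvious repair, deleting the restriction on Run-in Visit 3, would itself be faulty. It removes the only lower bound, so a value from Run-in Visit 2, scheduled 84 days before Day 1, could become the baseline. This objection is right, and the fix has to be bounded.

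**Conclusion.** The point holds as a minor one. The two baseline rules and the no-imputation rules together discard change scores that a pre-randomisation value, at most 7 days old under the protocol, could support.

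A reader might infer that any incomplete Day 1 assessment costs a subject every change score. It does not. Baseline is set per endpoint, so all four composites are lost only when a joint count or the patient global is missing; a lost CRP leaves CDAI and DAS28-ESR intact. Nor do the documents support any effect on the primary endpoint, or any bias between arms.

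The size rests on an assumed 1% to 10% of subjects with the relevant component missing on Day 1. That gives about 2.5 to 25 of 250 subjects and standard errors 0.5% to 5.4% larger in an affected change analysis. At the lower rates it is unlikely to alter a conclusion. The case for acting is that it costs almost nothing and settles the rule in advance.

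**What to change.** Amend the baseline definition in SAP 6.1 and the baseline row of the double-blind window table in Appendix A in the same way:

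- For each efficacy endpoint separately, use the last non-missing value after Run-in Visit 3 and no later than Study Day 1.
- If there is none, use the Run-in Visit 3 value, provided it was taken within the protocol's 7 days before Day 1.
- Otherwise the baseline stays missing, as now.

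Working per endpoint matters: a rule that required the whole Day 1 assessment to be complete would throw away a valid Day 1 CDAI because CRP was missing. The 7-day limit replaces the lower bound that a plain deletion would lose.

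Report by arm how many subjects use the fallback for each composite. If the sponsor intends the exclusion, the SAP should say so, give the reason, and report by arm how many subjects have no baseline.

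The cost is SAP wording and a small programming change, with no new data collection. The one trade-off is that a few baselines would come from the visit at which SDAI had to be 3.3 or less, equally in all arms.
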